3.5.1. Laboratory Data

Hematology and chemistry result will be programmatically graded according to the NCI CTCAE version 4.03 for relevant parameters. A shift summary of baseline grade by maximum post-baseline grade will be presented. Parameters which cannot be graded will be summarized relative to the normal range (ie, normal range high or normal range low). Additional details are provided in [Section 6.6.1](#).

3.5.2. Vital Signs

Vital signs data include weight, pulse rate, systolic blood pressure, and diastolic blood pressure. Measurements were only to be provided once per timepoint. If multiple assessments are provided per timepoint, the maximum value will be used for reporting. Additional details are provided in [Section 6.6.2](#).

3.5.3. Electrocardiograms

Three consecutive 12-lead ECGs pre-dose will be performed approximately 2 minutes apart to determine mean HR, RR, QT interval, PR interval, QRS complex, and QTcF at baseline. Additional ECGs may be collected as clinically indicated and as single ECGs. All ECG recordings will be listed. However, only the mean score calculated for the replicate measurements will be summarized. Additional details are provided in [Section 6.6.3](#).

4. ANALYSIS SETS (POPULATIONS FOR ANALYSIS)

Data for all participants will be assessed to determine if participants meet the criteria for inclusion in each analysis population prior to releasing the database and classifications will be documented per standard operating procedures.

Only participants who signed informed consent will be included in the analysis sets below.

Population	Description
Enrolled	All participants who sign the informed consent document.
Safety	All participants who receive at least 1 dose of dacomitinib.

5. GENERAL METHODOLOGY AND CONVENTIONS

All analyses will be performed at study participant data set release at the end of study, defined as 1 year after the last participant first visit (LPFV) date in the study.

5.1. Hypotheses and Decision Rules

5.1.1. Hypotheses and Sample Size

This is a single arm study with no statistical hypothesis testing. The primary objective of the trial is to evaluate the safety and tolerability of single-agent dacomitinib for the first-line treatment of participants in India with metastatic NSCLC with EGFR activating mutations.

This study will enroll a sufficient number of participants to ensure that 100 participants are treated with dacomitinib.

5.1.2. Decision Rules

Not applicable.

5.2. General Methods

5.2.1. Definition of Study Day

The study day for assessments occurring on or after the first dose of study treatment (eg, adverse event onset, tumor measurement) will be calculated as:

$$\text{Study day} = \text{Date of the assessment/event} - \text{start date of study treatment} + 1.$$

The study day for assessments occurring prior to the first dose of study treatment (eg, baseline characteristics, medical history) will be negative and calculated as:

$$\text{Study day} = \text{Date of the assessment/event} - \text{start date of study treatment}.$$

The study day will be displayed in all relevant data listings.

5.2.2. Definition of Cycle and Cycle Day

Cycle start and end dates are derived per participant. Treatment will be dispensed at the beginning of every 28-day cycle.

- For Cycle X, the actual cycle start date for each participant is:
 - The earliest start date of dosing (dose>0 at that visit) in Cycle X visit case report form (CRF) exposure page.

- For all but the last cycle.
 - Actual cycle stop date is calculated as the start date of the next cycle minus one day.
 - Actual cycle duration is calculated from Day 1 of a cycle to the day prior to Day 1 of the next cycle, as follows:

$$\text{Actual Cycle Duration (weeks)} = (\text{cycle stop date} - \text{cycle start date} + 1)/7.$$

- For the last cycle, actual cycle duration is calculated as follows:
 - $\text{Actual Cycle Duration (weeks)} = (\text{last date of study treatment} - \text{cycle start date} + 1)/7.$

The cycle day will be calculated as:

$$\text{Cycle day} = \text{Date of the assessment/event} - \text{cycle start date} + 1.$$

5.2.3. Definition of Start of New Anticancer Therapy

Start date of new anticancer therapy (drug, radiation, surgery) is used to determine the end of the on-treatment period (see [Section 3.5](#)) and for censoring in antitumor activity analyses (see [Section 6.2](#)).

The start date of new anticancer therapy is the earliest date after first dose of dacitinib amongst the following:

- Start date of anticancer drug therapy recorded in the ‘Concomitant Medications’ CRF pages with ‘Category of medication’ = ‘Follow-up Cancer Therapy’;
- Start date of radiation therapy recorded in ‘Radiation Treatment’ CRF pages with ‘Subcategory’ = ‘Curative in intent’;
- Surgery date recorded in ‘Non-drug Treatments’ CRF pages with ‘Category’ = ‘On-study Cancer Surgery’ and ‘Outcome of Procedure’ = ‘Resected’ or ‘Partially Resected’.

When start date of anticancer therapy is missing or partially missing, the imputation rules described in [Section 5.3.2.4](#) should be applied using ‘Concomitant Medications’, ‘Radiation Treatment’, and ‘Non-drug Treatments’ CRF pages.

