4.1. Inclusion Criteria

Participant eligibility should be reviewed and documented by an appropriate member of the investigator's study team before participants are included in the study.

Participants must meet all of the following inclusion criteria to be eligible for enrollment into the study:

1. Evidence of histologically or cytologically confirmed diagnosis of metastatic NSCLC with EGFR-activating mutations (exon 19 deletion mutation or L858R substitution mutation in exon 21) as detected by an appropriate test.
 - It is acceptable for participants with the presence of the exon 20 T790M mutation together with either EGFR-activating mutation (exon 19 deletion mutation or the L858R substitution mutation in exon 21) to be included in this study.
2. No prior treatment with systemic therapy for metastatic NSCLC. Completed neoadjuvant/adjuvant chemotherapy and/or combined modality chemotherapy/radiation therapy permitted only in cases in which there is a minimum of 12 months disease-free interval between completion of systemic therapy and recurrence of NSCLC. Prior treatment with an EGFR-TKI or other TKIs is not allowed.
3. Participants with asymptomatic CNS metastases (including participants controlled with stable or decreasing steroid use within the last 2 weeks prior to study entry) will be eligible.
4. Age ≥ 18 years.
5. ECOG PS of 0-2.
6. Adequate hematologic, renal and liver function as defined as:
 - a. ANC $\geq 1,000/\text{mm}^3$;

- b. Platelets $\geq 50,000/\text{mm}^3$;
 - c. Hemoglobin ≥ 8 g/dL;
 - d. Estimated creatinine clearance ≥ 30 mL/min as calculated using the method standard for the institution;
 - e. Total serum bilirubin $< 1.5 \times \text{ULN}$;
 - f. AST and ALT $\leq 2.5 \times \text{ULN}$ ($\leq 5.0 \times \text{ULN}$ in case of liver metastases).
7. Acute effects of any prior therapy resolved to baseline severity or to CTCAE Grade < 1 except for AEs that in the investigator's judgment do not constitute a safety risk for the participant.
 8. Serum or urine pregnancy test (for females of childbearing potential) negative at Screening. Female participants of childbearing potential and at risk for pregnancy must agree to use a highly effective method of contraception from the time of the first negative pregnancy test at Screening, throughout the study and for at least 17 days after the last dose of assigned treatment.

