5.6.1. Prohibited Concomitant Treatments

Concomitant use with a PPI decreases dacomitinib concentrations, which may reduce dacomitinib efficacy. The concomitant use of PPIs with dacomitinib should be avoided. As an alternative to PPIs, use locally-acting antacids or an H₂-receptor antagonist. Dacomitinib should be administered at least 6 hours before or 10 hours after taking an H₂-receptor antagonist.

Concomitant use of dacomitinib increases the concentration of drugs that are CYP2D6 substrates which may increase the risk of toxicities of these drugs. The concomitant use of dacomitinib with CYP2D6 substrates should be avoided as minimal increases in concentration of the CYP2D6 substrate may lead to serious or life-threatening toxicities.

Other Antitumor or Experimental Drugs

No additional systemic antitumor therapy will be permitted while participants are receiving a study therapy.

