- ‘Cystic lesions’ thought to represent cystic metastases can be considered as measurable lesions, if they meet the definition of measurability described above. However, if non-cystic lesions are present in the same participant, these are preferred for selection as target lesions.

Lesions with prior local treatment:

- Tumor lesions situated in a previously irradiated area, or in an area subjected to other loco-regional therapy, are usually not considered measurable unless there has been demonstrated progression in the lesion.

Solitary lesions:

- If a measurable disease is restricted to a solitary lesion, its neoplastic nature should be confirmed by cytology/histology.

Recording Tumor Measurements

All measurable lesions up to a maximum of 2 lesions per organ and up to 5 in total and representative of all involved organs should be identified as target lesions and measured and recorded at baseline and at the stipulated intervals during treatment. Target lesions should be selected on the basis of their size (lesions with the longest diameters) and their suitability for accurate repetitive measurements (either by imaging techniques or clinically).

The longest diameter will be recorded for each target lesion. The sum of the longest diameter of all target lesions will be calculated and recorded as the baseline sum diameter to be used as reference to further characterize the objective tumor response of the measurable dimension of the disease during treatment.

One (1) exception to the above described approach is related to pathological lymph nodes. Pathological lymph nodes are defined as measurable lesions and may be identified as target lesions if the criterion of a short axis of ≥ 15 mm by CT scan is met. Only the short axis of these nodes will contribute to the baseline sum. Nodal size is normally reported as two dimensions in the plane in which the image is obtained (for CT scan this is almost always the axial plane; for MRI the plane of acquisition may be axial, sagittal or coronal). The smaller of these measures is the short axis.

A sum of the diameters (longest for non-nodal lesions, short axis for nodal lesions) for all target lesions will be calculated and reported as the baseline sum diameters. The baseline sum diameters will be used as reference to further characterize any objective tumor regression in the measurable dimension of the disease.

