6.5.5. Subsequent anticancer therapies

The following analyses will be based on the Safety Set.

Subsequent anticancer therapies are defined as medications/procedures entered in the 'Concomitant Medications' (with 'Category of Medication' = 'Follow-up Cancer Therapy'), 'Radiation Treatment' (with 'Subcategory' = 'Curative in intent'), and 'Non-drug Treatments' (with 'Category' = 'On-study Cancer Surgery' and 'Outcome of Procedure' = 'Resected' or 'Partially Resected') CRF pages. The number and percentage of participants within each category (medication therapy, radiation therapy, and surgeries) will be provided.

Medications will be coded using the WHO Drug coding dictionary and will be tabulated by preferred term in descending order of frequency.

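### SAP 5.2.3 ignores non-curative radiotherapy, so the plan permits shrinkage of a target lesion irradiated on study to count towards confirmed ORR

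*SAP*

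**What the plan says.** SAP 5.2.3 derives one date, the start of new anticancer therapy. It ends the on-treatment period and is also used "for censoring in antitumor activity analyses". Three sources feed it:

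- follow-up anticancer drugs;
- radiotherapy, by the "Start date of radiation therapy recorded in" the Radiation Treatment CRF pages, and only where the subcategory is curative in intent;
- on-study cancer surgery with "Outcome of Procedure’ = ‘Resected’ or ‘Partially Resected", where intent plays no part.

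That date is the only therapy-based stop for best overall response and ORR (SAP 2.1.2, 3.2.1, 6.2.1) and the only therapy-based censoring reason for DoR (SAP 6.2.2). The table of subsequent therapies in SAP 6.5.5 applies the same filter: "Radiation Treatment' (with 'Subcategory' = 'Curative in intent".

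Protocol 4.1 requires "Evidence of histologically or cytologically confirmed diagnosis of metastatic NSCLC with EGFR-activating mutations". Protocol 5.6.1 limits other antitumor treatment as follows: "No additional systemic antitumor therapy will be permitted while participants are receiving a study therapy". It does not mention on-study radiotherapy.

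On locally treated lesions, Protocol Appendix 1 says: "Tumor lesions situated in a previously irradiated area, or in an area subjected to other loco-regional therapy, are usually not considered measurable", unless the lesion has since progressed.

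**The concern.** The secondary estimand is the treatment effect of dacomitinib. Local treatment of a target lesion can shrink it for reasons unrelated to the drug. The SAP recognizes this for surgery: removing part of a lesion closes the response window whatever the purpose. Irradiating the same lesion closes it only if the record is labelled curative. In a wholly metastatic population, much on-study radiotherapy can be expected to carry another label.

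Radiotherapy is a realistic event here. The exclusion criteria set washouts for palliative, stereotactic brain and whole-brain radiation, and participants with asymptomatic CNS metastases may enroll.

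What is at stake is the reading of ORR in a single-arm study, where no comparator would share the same distortion. The table in SAP 6.5.5 would not reveal the problem, because it drops the same records. SAP 6.5.4 summarizes concomitant non-drug treatments by coded term. It does not say whether Radiation Treatment records enter that table, and it plans no breakdown by irradiated site or intent.

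**Working it through.** **1. Does any other rule close the gap?** The texts, set side by side:

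- Appendix 1 classifies lesions as measurable or not at baseline. Its clause on irradiated areas belongs to that step and gives no rule for a target lesion irradiated later.
- SAP 5.2.7 treats any time point with an investigator response of CR, PR, SD, non-CR/non-PD or PD as adequate. SAP 6.2.1 builds best overall response from those investigator responses. There is no lesion-level rule.
- Appendix 1, Table 3 returns NE when not all target lesions are evaluated, non-target lesions are non-PD and there is no new lesion. An investigator may use this route for an irradiated lesion, but nothing requires it.

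The outcome therefore depends on the individual investigator.

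**2. When is ORR exposed?** Only if a target lesion is irradiated before the response is confirmed. Scans are every 12 weeks ±1 week and confirmation needs at least 4 weeks (Protocol 7.1.1). For a response first seen at week 12, confirmation comes no earlier than week 12 + 4 = 16, or at about week 24 if left to the next scheduled scan. Radiotherapy after that cannot change ORR.

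**3. Can one irradiated lesion produce a PR?** PR needs at least a 30% fall in the sum of target diameters (Appendix 1). Assumed sizes: sum 80 mm, of which one lesion is 30 mm. It shrinks by 80% after irradiation and the others do not change.

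- New sum = 30 × (1 − 0.80) + 50 = 6 + 50 = 56 mm.
- Fall = (80 − 56)/80 = 30.0%, which meets PR.

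**4. The plan's own precision figure.** Protocol 9.2 gives a maximum standard error of 0.05 with 100 participants. √(0.5 × 0.5/100) = 0.050, which reproduces it.

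**5. Effect on ORR.** With N = 100, each affected participant adds 1/100 = 1 point. The documents give no expected ORR and no count of affected participants, k, so both are assumptions here. The interval is the planned Wilson score interval, with z = 1.96:

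[p + z²/2n ± z√(p(1−p)/n + z²/4n²)] / (1 + z²/n)

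For p = 0.70: (0.70 + 0.0192)/1.0384 = 0.6926 and 1.96 × √(0.0021 + 0.000096)/1.0384 = 0.0885, giving 60.4 to 78.1.

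| ORR as planned | k | ORR without those k |
|---|---|---|
| 70% (60.4–78.1) | 1 | 69% (59.4–77.2) |
| 70% | 2 | 68% (58.3–76.3) |
| 70% | 5 | 65% (55.3–73.6) |
| 50% (40.4–59.6) | 5 | 45% (35.6–54.8) |
| 80% (71.1–86.7) | 5 | 75% (65.7–82.5) |

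**6. How large might k be?** Inflation in points = 100 × r × q × s, where r is the share irradiated on study, q the share of those with a target lesion in the field, and s the share of those who respond only because of it. All three are assumptions.

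- Low: 100 × 0.05 × 0.10 × 0.25 = 0.125.
- Middle: 100 × 0.10 × 0.25 × 0.50 = 1.25.
- High: 100 × 0.20 × 0.50 × 1.00 = 10.

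For comparison, the half-width of the interval is (86.7 − 71.1)/2 = 7.8 points at 80% and (59.6 − 40.4)/2 = 9.6 points at 50%.

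**7. DoR.** Under SAP 6.2.2, Table 2, a responder irradiated before formal progression who then progresses or dies within 26 weeks of the last adequate assessment is an event. Censoring at the last assessment before radiotherapy would remove that event. If radiotherapy goes mainly to those close to failure, the censoring is informative and can lengthen the Kaplan-Meier median. Leaving the rule alone lets radiotherapy delay progression, which also lengthens DoR. The net direction cannot be settled from the documents, and they give no DoR input from which to compute a size.

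**The case against.** Not counting palliative radiotherapy as new anticancer therapy is a coherent, pre-specified choice. It keeps non-target treatment, such as for bone pain, from ending follow-up of response. That stands, and the change below leaves it alone.

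The CRF is not in the documents. Ablative treatment of limited metastases may well be coded as curative, in which case the existing rule applies. So one cannot say that the curative branch will almost never operate.

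A reader might infer that the SAP contradicts RECIST by continuing to use irradiated lesions. The documents do not support this: the Appendix 1 clause concerns measurability at baseline and says usually, and the SAP simply takes the investigator's overall response. For the same reason one cannot say that shrinkage from radiotherapy is credited to dacomitinib, only that it can be.

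A reader might also infer that the bias always favors dacomitinib. For ORR, any error of this kind is upward. For DoR the claim fails, because the obvious correction, censoring at radiotherapy, may itself lengthen the median.

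**Conclusion.** The gap in the ORR rule is real but minor. Non-curative irradiation of a target lesion before confirmation is neither prohibited, nor treated as new anticancer therapy, nor given a scoring rule, whereas partial resection of the same lesion would end the window. The size is 1 point of ORR per affected participant at N = 100. The number affected is unknown and may be zero; any range, including 1 to 5 points, is pure assumption and lies inside the half-width of the planned interval. There is no hypothesis test or decision rule, so nothing formal changes, and the primary AE endpoint does not rest on this point. The documents do not support extending the criticism to the main DoR censoring rule.

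**What to change.** For ORR only, add to SAP 3.2.1 and 6.2.1, with a matching line in the ORR estimand in 2.1.2: a CR or PR first documented or confirmed only after radiotherapy of any intent to a target lesion does not count as a confirmed response; a response confirmed before the radiotherapy stands.

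Leave unchanged the main DoR censoring rule, the handling of radiotherapy to non-target sites, and the AE on-treatment window. Add a DoR sensitivity analysis that censors at target-lesion radiotherapy, and a listing of all on-study radiotherapy by site and intent. These are analysis changes only; nothing about participant care is proposed.

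Costs:

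- ORR may be slightly lower, and someone who would have responded to the drug alone but was irradiated before confirmation is lost as a responder. Such participants also leave the DoR set, which is limited to confirmed responders. With measurable disease and an SD-or-better assessment at 6 weeks or later, they would fall to SD under the existing rules.
- The irradiated site must be available from the Radiation Treatment CRF page. If it is not, the ORR rule cannot be programmed as written and a listing by intent is the fallback.

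Settle the wording before the database is released.

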5.2.4. Date of Last Contact

The date of last contact will be derived for participants not known to have died at the end of study using the latest complete date (ie, imputed dates will not be used in the derivation) among the following:

- All participant assessment dates eg, tumor assessments;

- Start and stop dates of concomitant therapies including non-drug treatments or procedures;
- Start and end dates of anticancer therapies administered after study treatment discontinuation including systemic therapy, radiation, and surgeries;
- AE start and end dates;
- Date of first and last dose;
- Vital sign, ECG and laboratory assessment;
- Date of discontinuation on disposition CRF pages (do not use if reason for discontinuation is lost to follow-up or death).

Only dates associated with actual examinations of the participant will be used in the derivation. Assessment dates after the end of study will not be applied to derive the last contact date.

5.2.5. Tumor Assessment Date

The date of tumor assessment at each nominal timepoint as provided by the investigator on the Investigator Overall Tumor Assessment (IOTA) CRF will be utilized for the antitumor activity analyses.

5.2.6. Adequate Baseline Tumor Assessment

Adequate baseline is defined using the following criteria:

- All baseline assessments must be within 35 days prior to and including the date of first dose of dacomitinib.
- All documented lesions must have non-missing assessments (ie, non missing measurements for target lesions and non missing lesions status at baseline for non-target lesions).
- Measurable disease at baseline, defined as at least one non-nodal target lesion with longest diameter ≥ 10 mm by computerized tomography (CT) or magnetic resonance imaging (MRI) or calliper for superficial lesion, or at least one malignant lymph node with short axis ≥ 15 mm.

5.2.7. Adequate Post-baseline Tumor Assessment

An adequate assessment is defined as an assessment where a response of CR, PR, Stable Disease (SD), non-CR/non-PD, or PD has been provided by the investigator. Timepoints where the response is not evaluable or no assessment was performed will not be used for determining the censoring date.

5.2.8. Nominal and Unscheduled Visits

For all algorithms and analyses, visit labels as specified on the CRF will be used as the nominal timepoint (ie, assessment will not be slotted).

Unless otherwise specified, unscheduled assessments will not be displayed in summary tables by nominal visit/timepoint. Unscheduled assessments will be used when deriving baseline and worst case on-treatment for adverse events, laboratory and vital signs assessments. Additionally, unscheduled tumor assessments will be used for antitumor activity analyses (eg, defining date of progression/censoring, best overall response, date of last contact).

5.2.9. Standard Derivations and Reporting Conventions

The following conversion factors will be used to convert days into weeks, months or years:
1 week = 7 days, 1 month = 30.4375 days, 1 year = 365.25 days.

Demographics and physical measurements:

- Age [years]:
 - (year of given informed consent - year of birth).

For reporting conventions, mean and median should generally be displayed one more decimal place than the raw data and standard deviation (Std Dev) should be displayed to two more decimal places than the raw data. Percentages will be reported to one decimal place. The rounding will be performed to closest integer/first decimal using the common mid-point between the two consecutive values eg, 5.1 to 5.4 will be rounded to an integer of 5, and 5.5 to 5.9 will be rounded to an integer of 6.

